8.5.4 Follow-up of Study Subjects Who Discontinue Device Use

Discontinuation of study device use does not constitute discontinuation from the study, and the study procedures should be completed as indicated by the Study Schedule of Activities. If a clinically significant finding is identified, including, but not limited to, changes from baseline, after enrollment, the participating clinical trial site PI or qualified designee will determine if any change in subject management is needed. Any new clinically relevant finding will be reported as an AE.

9 STUDY ASSESSMENTS AND PROCEDURES

9.1 Screening Assessments

9.1.1 Screening Procedures

At the screening visit, and prior to any other study-related activities, designated study personnel will provide the subject with detailed study information and will obtain written informed consent (see section 11.1.1 for more details).

Subject numbers will be assigned with the three-digit numerical site number beginning with numbers greater than two hundred (e.g. 201) followed by an alphanumeric protocol identifier (P20) and finally a three digit unique numerical identifier assigned with each new subject (e.g. 001).

Example Subject Number: 201-P20-001

COVID-19 Screening

Subjects who identify with symptomatology associated with COVID-19 will be first screened by taking a nasal culture and analyzed for the presence of SARS-CoV-2 by an FDA authorized SARS-CoV-2 antigen test (e.g. BD Veritor™ Plus System, AccessBio Carestart). These systems allow for rapid detection of SARS-CoV-2 via immunoassay for the direct and qualitative detection of SARS-CoV-2 antigens. Subjects presenting at the time of screening that have tested positive via a SARS-CoV-2 rapid antigen test within the past 24 hours and can provide documentation confirming proper identification, the date of the test and testing location, positivity of the result, and name/identity of the assay used to generate the result, are also eligible for enrollment.

Eligible subjects for enrollment must present with uncomplicated COVID-19 and have at least two moderate or severe symptoms (cough, sore throat, nasal congestion, headache, unexplained chills and/or sweats, myalgia, fatigue, nausea (with or without vomiting) and consent to be randomized within 3 days of first symptom onset. The subjects will self-assess their COVID-19 symptoms as none (0), mild (1), moderate (2), or severe (3) during screening as part of a disease assessment questionnaire.

- Subjects with the presence of at least one moderate symptom and either a) a fever with an oral temperature of at least 100.5 °F or b) shortness of breath/difficulty breathing on exertion (e.g., walking, going up and down stairs) are also eligible for enrollment.
 - If subjects present with dyspnea on exertion or at rest, SpO₂ should be measured and recorded. See I/E criteria for eligibility of enrollment.
 - For demographic purposes, all subjects reporting shortness of breath at baseline will be categorized as having 'Moderate COVID-19' consistent with NIH guidelines (Section 7.0).

Subjects with COVID-19 disease with signs and symptoms reported > 72 hours from onset will be given instructions to see their primary care physician or be advised to seek potential treatment (if eligible) at a local antibody infusion center. Additionally, subjects will also be asked to report if they have been previously diagnosed with COVID-19 via a laboratory confirmed diagnostic test and whether or not they report that they have been previously vaccinated with at least one dose of COVID-19 vaccine. The month and year for one or both events will be recorded. The complete COVID-19 disease assessment will include vital signs recorded as part of general screening, ask subjects to assess their loss of taste and loss of smell (binary assessments at each assessment*), report if they experience any shortness of breath on exertion, and pose the following patient-reported global impression assessments on Days 8 and 14:

a) In the past 24 hours, have you returned to your usual health (before your COVID-19 illness)? Yes or No

b) In the past 24 hours, have you returned to your usual activities (before your COVID-19 illness)? Yes or No

* COVID-related loss of sense of taste and loss of sense of smell are well understood to normalize over a prolonged period of time given the neurological etiology, long after SARS-CoV-2 has been eliminated from the body. As these signs of COVID-19 have been reported to vary with each variant, this information is being collected for demographic purposes and will be assessed only as part of the qualitative patient reported global assessment.

General Screening

Some or all of the following assessments are performed during the screening visit to determine eligibility requirements as specified in the inclusion and exclusion criteria:

- Obtain subject-reported medical history focusing on conditions per protocol exclusion criteria.
- Review all pre-study medications, vitamins, supplements, and therapies up to 14 days prior to the start of screening that could impact the use of, or response to, the device and record on the appropriate source document. The use of any medications to treat some of the COVID-19-related symptoms (e.g., analgesics, antipyretics) should be recorded and the name of medication, dose, dosage form, and date and time(s) of administration should be reported. Antibiotics are not indicated as a treatment for COVID-19 and prior use of antibiotics (e.g. tetracycline, azithromycin) should be documented accordingly. Subjects receiving antibiotics for treatment of COVID-19 must discontinue use prior to study enrollment and this information should be documented. Subjects should be informed not to take antibiotics or other medications purported to treat COVID-19 (such as hydroxychloroquine or ivermectin) during their participation in the study. Antibiotic treatment of a bacterial infection during screening is a protocol exclusion because of the existence of an active concurrent disease. During the study, the decision to prescribe antibiotics is a clinical decision that should be made by the subject's primary care provider outside of the protocol. Such use, and the reason for such use, will be documented. While actively participating in the study, if antibiotics or other putative COVID-19 treatment drugs are

prescribed for treatment of COVID-19, volunteers must not use these drugs if they desire to remain in the active protocol. Subjects presenting at baseline with a fever of 100.5 or higher as measured via oral temperature will be advised to take acetaminophen for use in accordance with its labeling instructions. There is no prohibition on the use of analgesics for symptomatic treatment of pain. Any such use should be recorded on the concomitant medication form along with reason for use.

- Measure oxygen saturation via pulse oximeter
- Measure vital signs (HR, BP, RR, and oral temperature) and height and weight for determination of BMI.
- Perform full physical examination which will include assessments of the following organs and organ systems: skin, head, ears, eyes, nose, and throat (HEENT), neck, lungs, heart, liver, spleen, abdomen, extremities, lymph nodes (axillary and cervical), and nervous system.
- Obtain blood and urine for clinical screening laboratory evaluations:
 - Comprehensive Metabolic Panel (fasting or non-fasting)
 - CBC with differential
 - Absolute Neutrophil Count to Absolute Lymphocyte Count Ratio (N/L ratio) ≥ 4.5 may be a clinically significant risk factor for progression to severe COVID-19
 - Red cell distribution width (RDW) ≥ 15 may be a clinically significant risk factor for progression to severe COVID-19.
 - Urine pregnancy test (in women of childbearing potential)
 - Anti-SARS-CoV-2 Spike, IgG
- Review inclusion and exclusion criteria.

The overall eligibility of the subject to participate in the study will be assessed once all screening values are available. The screening process can be suspended prior to complete assessment at any time if exclusions are identified by the study team.

Subjects with COVID-19 disease diagnosed via a rapid antigen test with signs and symptoms reported ≥ 72 hours from onset are not eligible for enrollment.

Study subjects who qualify for inclusion will be immediately randomized for their day 1 visit.

If a physiologic parameter, e.g., vital signs, is outside of the protocol-specified range, then the measurement may be repeated once if, in the judgment of the participating clinical site PI or appropriate sub-investigator, the abnormality is the result of an acute, short-term, rapidly

reversible condition (e.g., stress, anxiety or “white coat syndrome”) or other source of error. A physiologic parameter may also be repeated if there is a technical problem with the measurement caused by malfunctioning, or an inappropriate measuring device (i.e., inappropriate-sized BP cuff).

A subject may be re-screened if a protocol eligibility criterion that is not met at the initial time of screening, will be met by rescreening of all assessments within the next 24 hours using the same subject number, provided their number of days since symptom onset remains ≤ 3 days.

No subjects may be screened more than twice due to a screening failure result as defined above.

Subjects will be provided the results of abnormal clinical laboratory test values or abnormal clinical findings necessitating follow-up with their primary care provider.

9.1.2 Procedures for Clinically Significant Laboratory Values or Findings

If in the judgement of the PI the finding poses a previously unknown risk to the subject or leads to a diagnosis of a disease or condition that would have disqualified the subject for enrollment, the subject will be withdrawn from the study immediately.

All clinically significant findings that occur post randomization and after the first use of the RD-X19 device will be considered TEAEs. Clinically significant lab findings based on Visit 1 lab draws are considered Medical History and not Adverse Events.

9.1.3 Bio-specimen Collection

At Baseline and on days 3, 5, 8, and 14, subjects will provide one saliva specimen and one nasopharyngeal swab for virology endpoint assessments. Biospecimens will be collected, preserved, and shipped to a central lab for assessment of SARS-CoV-2 mRNA via RT-qPCR as outlined in the EB-P20-01 Laboratory Manual. To minimize the potential impact of diurnal variation on saliva excretion rates, a subject with a morning baseline visit (before 12 pm), should target morning follow-up visits and subjects with an afternoon baseline visit (after 12 pm) should target afternoon follow-up visits. If a visit must switch from morning to afternoon or vice versa, the visit must occur within ± 1 hour of the noon timepoint, e.g., if the previous visit is at 8:00 am and the next visit is at 12:45 pm this would be acceptable; if the previous visit is at 11 am and the next visit is at 2:00 pm, then this would be considered a deviation.

Optionally, the sponsor may perform additional genetic sequencing on one or both baseline specimens (saliva or nasopharyngeal) to obtain prevalence of variants of interest (VOI) or variants of concern (VOC) in the study population. Specific variants to be identified include B.1.1.7 (UK), B.1.351 (South Africa), B.1.427 (CA), B.1.429 (CA), P.1 (Brazil), and B.1.617.2 (India), and any others that are classified as VOI or VOC during the study.

A second saliva sample (third biospecimen), will be collected at baseline and on days 8 and 14, and at Sponsor's option shipped to a third party laboratory to evaluate the effects of RD-X19 on

the microbial flora of the oral microbiome. Change in α and β diversity in microbial flora from baseline will be analyzed by 16S rRNA subunit analysis from saliva samples.

9.2 Safety and Other Assessments

Study procedures are specified in protocol section 4.3 Schedule of Activities. A study clinician, licensed to make medical diagnoses as the participating clinical site PI or appropriate sub-investigator, will be responsible for all study-related medical decisions.

- Medical history:
 - A complete medical history will be obtained by interview of subjects at the screening visit. Subjects will be queried regarding a history of significant medical disorders of the head, ears, eyes, nose, throat, mouth, cardiovascular system, lungs, gastrointestinal tract, liver, pancreas, kidney, urologic system, nervous system, blood, lymph nodes, endocrine system, musculoskeletal system, skin, and genital/reproductive tract. A history of any allergies, cancer, immunodeficiency, psychiatric illness, substance abuse, and autoimmune disease will be solicited.
 - At all subsequent visits, an interim medical history will be obtained by interview of subjects and any changes since the previous clinic visit will be noted. The interim medical history should include an assessment for new medical conditions and symptoms suggestive of an AE.
- Physical examination:
 - A full physical examination will be performed at the screening visit and on days 8 and 14, and a symptom-directed (targeted) physical examination will be performed if indicated during other clinic visits
 - A full physical examination will include assessments of the following organs and organ systems: skin, HEENT, neck, lungs, heart, liver, spleen, abdomen, extremities, lymph nodes (axillary and cervical), and nervous system.
 - Height and weight will be measured, and BMI calculated, at the screening visit only.
 - A symptom-directed (targeted) physical examination will be performed if indicated during other scheduled clinical site visits.

- Targeted physical examinations will primarily focus on assessment of signs and symptoms suggestive of AEs and an examination of the oral cavity that demonstrates findings of thrush or other pathology that may indicate clinically-relevant changes to the oral microbiome. Interim or unscheduled physical examinations will be performed at the discretion of the participating clinical site PI or appropriate sub-investigator, if necessary, to evaluate AEs.
- Subjects will be observed in the clinic for at least 30 minutes post the first RD-X19 illumination. The oropharynx and surrounding tissues will be examined. Reactogenicity assessments will be performed on Day 1 in the clinic on days 3, 5, 8, and 14 by subjects' diary card entries. Interim or unscheduled targeted physical examinations will be performed, if necessary, to evaluate TEAEs.
- Vital signs:
Vital sign measurements will include systolic and diastolic BP, HR, breaths per minute, oral temperature and oxygen saturation via a pulse co-oximeter. Vital signs will be measured at timepoints specified in protocol section 4.3. Subjects must not eat or drink anything hot or cold within 10 minutes prior to taking their oral temperature or using the RD-X19 device. All subjects will be issued thermometers and small pulse oximeters to measure oral temperature and O₂ saturation on a twice daily basis and record the results on their diary card.
- Clinical laboratory evaluations:
 - Fasting is not required before collection of clinical laboratory evaluations.
 - Urine pregnancy test will be performed locally by the site laboratory at the screening visit. Results must be confirmed as negative prior to randomization on Day 1 and allocation and use of the RD-X19 device.
 - Clinical laboratory evaluations CMP and CBC (diff) will be performed locally by the site selected laboratories.
 - Clinical safety laboratory evaluations will be performed locally by the site laboratory.

- Blood will be collected at timepoints specified in the protocol section 4.3.
- Methemoglobin will be measured as stipulated in the study procedures table using the Massimo® non-invasive pulse oximetry device.
- Anti-Spike IgG will be measured at screening/baseline and on Day 14.
- Absolute Neutrophil Count to Absolute Lymphocyte Count Ratio (N/L ratio) and Red cell distribution width (RDW) will both be recorded from the CBC panel.
- Diary Cards:
 - Subjects will be instructed to fill out diary cards twice daily to assess their symptoms associated with disease progression and record the number of treatments completed. Each of the eight symptoms will be rated on a 4-point scale from none (0) to severe (3). Temperature and oxygen saturation will also be measured and recorded via devices provided by site personnel and taken home by the subject. Subjects will also be asked if they experience any shortness of breath. Reminders will be sent to each subject twice daily via an appropriate communication platform (e.g. text messaging) and up to date diary cards should be presented at each clinical visit to be eligible for subject payments. Between visits on Days 2 and 4, to enhance safety monitoring and reinforce adherence to at-home study procedures, each subject will be contacted via phone and verbally go through diary procedures and document any AEs.
- Severe COVID-19 Clinical Outcomes
 - There is a small amount of risk that subjects with mild-to-moderate COVID-19 may have an unknown health problem or co-morbidity at the time of screening that can lead to rapid worsening of condition or hospitalization during study. Worsening of condition will be characterized by study subjects who experience COVID-19 progression defined by an increase of the composite COVID-19 severity score greater than baseline at any point in the study on or after day 3.

- Medically attended visits as a result of severe COVID-19 clinical outcomes will be aggregated into the following categories:
 - 1) those who require medical attention attributed to COVID-19;
 - 2) those who progress to severe disease with respiratory rate >30/minute and/or O2 saturation ≤93% on room air or FiO2 ≥300% with any respiratory distress;
 - 3) those who require hospitalization for severe COVID-19;
 - 4) those who require endotracheal ventilation or ECMO with or without the use of solumedrol; and
 - 5) those who die.
- Subjects with a primary care, urgent care, or emergency room visit that are not hospitalized as a result of their medical consultation, may continue treatment with the investigational device and should attend regularly scheduled follow up visits per protocol. Subjects that are admitted to the hospital should discontinue all treatment in lieu of standard of care for severe/critical COVID-19 illness.

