4.1.2 Study Design

Subjects will provide written informed consent prior to initiating any screening procedures. Subjects meeting all screening criteria will be eligible for enrollment and randomization into the study. Subjects with COVID-19 disease with signs and symptoms reported > 72 hours from onset will be given instructions to see their primary care physician or be advised to seek potential treatment (if eligible) at a local antibody infusion center.

This Phase II, dose finding portion of the trial is targeting to enroll a minimum of 60 volunteers with 30 in each of at least two dosing cohorts (20 assigned to RD-X19 and 10 assigned to sham per cohort, 2:1 randomization).

Cohort A will begin with 24 J/cm² per treatment, administered 2X/Day for duration of 7 days. Once 80% of subjects (n=24) in Cohort A complete the Day 8 visit and no predefined safety signals as outlined in the study pausing/stopping criteria have been observed, Cohort B, 32 J/cm² per treatment will start enrollment. In the event device-related serious adverse events or patterns of device-related adverse events, including application site reactions, are observed in Cohort A, and based on the review and recommendation of the external safety monitoring committee (SMC) of unblinded data, the study may proceed with enrollment and dosing in Cohort C, 16 J/cm² per treatment in keeping with SMC recommendations. An illustration of the ascending (or descending) dose finding design is provided below.

Cohort A: RD-X19 24 J/cm² vs. Sham

[figure not shown]
(5 minute treatment, 2X/Day for a duration of 7 days)

Cohort B: RD-X19 32 J/cm² vs. Sham

(5 minute treatment, 2X/Day for a duration of 7 days)

Cohort C: RD-X19 16 J/cm² vs. Sham

(5 minute treatment, 2X/Day for a duration of 7 days)

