Subjects who test positive for SARS-CoV-2 antibodies from blood draws at baseline will continue treatment for the duration of the study, undergo all assessments, and be excluded from the modified full analysis set (mFAS). For each subject testing positive for SARS-CoV-2 antibodies at baseline, one additional subject will be enrolled and randomized into the study for each of Cohorts A and B (*does not apply to optional enrollment period once the dose has been selected for the additional 150 subjects).

Safety and tolerability (local reactogenicity) will be assessed actively on each clinic visit by review of study subjects' daily diary cards for potential TEAEs, and oral cavity examination and targeted physical examination, as required.

Metabolic, liver, kidney and hematological laboratory evaluations will be performed at screening and at Day 14 or early termination (and potentially during unscheduled) clinic visits.

Subjects will be instructed to fill out diary cards twice daily to assess their symptoms associated with disease progression and record the number of treatments completed. Each of the eight symptoms will be rated on a 4-point scale from none (0) to severe (3) and a summary severity average will be calculated. Twice daily oral temperatures and oxygen saturation levels (SpO2) will also be recorded on the diary from readings taken by at-home devices dispensed to each subject. Reminders will be sent to each subject twice daily via an appropriate communication platform (e.g. text messaging).

Study Subject safety will be monitored throughout the study by the Investigator and supported by regular review by the Medical Monitor and a Chartered Safety Monitoring Committee.

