9.2.2 Solicited Treatment Emergent Adverse Events - Reactogenicity

Solicited TEAEs are anticipated TEAEs for which consistent collection of information is desired. Study clinicians will follow and collect resolution information for any reactogenicity symptoms that are not resolved during the active study period.

Solicited TEAEs (i.e., reactogenicity) will be collected by direct questioning of study subjects and recorded on the appropriate source document and e-CRF during the entire course of the study.

For this study, solicited AEs include:

- Illumination site Pain
- Illumination site Erythema
- Illumination site Edema/Induration
- Any other pain, redness, swelling or lesion of the oral mucosa

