	n (%) subject with illumination site erythema	XX (XX.X)	XX (XX.X)	XX (XX.X)	XX (XX.X)
	n (%) subject with illumination site Edema/Induration	XX (XX.X)	XX (XX.X)	XX (XX.X)	XX (XX.X)
	n (%) subject with other pain, redness, swelling, lesion of the oral mucosa	XX (XX.X)	XX (XX.X)	XX (XX.X)	XX (XX.X)
Visit 3 / Day 5	...				
Visit 4 / Day 8	...				
Visit 5 / Day 14/ ET	...				

Note: Reactogenicity assessed after illumination for treatments performed at the site on Visits 1, 2, and 3.

Source: Listing 16.x.x

O:\Studies\EmitBio\EB-P20-01\Biometrics\Programs\Tables\xxx.sas ran on Month Day, Year at hh:mm on data from Month Day, Year.

Table 14.3.3 – Oropharyngeal Assessment by Visit for Safety Population

Study Visit	Category	RD-X19 from Final Cohort n (%)	RD-X19 from Cohort A n (%)	Pooled RD-X19 n (%)	Pooled Sham n (%)
Overall*	N	XX	XX	XX	XX
	Normal	XX (XX.X)	XX (XX.X)	XX (XX.X)	XX (XX.X)
	Abnormal	XX (XX.X)	XX (XX.X)	XX (XX.X)	XX (XX.X)
Visit 1 / Day 1	N	XX	XX	XX	XX
	Normal	XX (XX.X)	XX (XX.X)	XX (XX.X)	XX (XX.X)
	Abnormal	XX (XX.X)	XX (XX.X)	XX (XX.X)	XX (XX.X)
Visit 2 / Day 3	N	XX	XX	XX	XX
	Normal	XX (XX.X)	XX (XX.X)	XX (XX.X)	XX (XX.X)
	Abnormal	XX (XX.X)	XX (XX.X)	XX (XX.X)	XX (XX.X)
Visit 3 / Day 5	...				
Visit 4 / Day 8	...				
Visit 5 / Day 14/ET	...				

\*For Overall, Normal category includes subjects with a normal result for all visits; Abnormal category includes subjects with an abnormal result at any visit. Note: Oropharyngeal assessments performed within 30 minutes after exposure for treatments performed at the site on Visits 1, 2, and 3.

Source: Listing 16.x.x

O:\Studies\EmitBio\EB-P20-01\Biometrics\Programs\Tables\xxx.sas ran on Month Day, Year at hh:mm on data from Month Day, Year.

Table 14.3.4.1 – Vital Signs (Systolic Blood Pressure (mmHg)) by Visit for Safety Population

Study Visit	Category	Statistics	RD-X19 from Final Cohort (N=XX)	RD-X19 from Cohort A (N=XX)	Pooled RD-X19 (N=XX)	Pooled Sham (N=XX)
Visit 1 / Day 1 (Baseline)	Actual Value	N	XX	XX	XX	XX
		Mean ± SD	XX.X ± XX.X	XX.X ± XX.X	XX.X ± XX.X	XX.X ± XX.X
		Median	XX.X	XX.X	XX.X	XX.X
		Min, Max	XX, XX	XX, XX	XX, XX	XX, XX
Visit 2 / Day 3	Actual Value	N	XX	XX	XX	XX
		Mean ± SD	XX.X ± XX.X	XX.X ± XX.X	XX.X ± XX.X	XX.X ± XX.X
		Median	XX.X	XX.X	XX.X	XX.X
		Min, Max	XX, XX	XX, XX	XX, XX	XX, XX
	Change from Baseline	Mean ± SD	XX.X ± XX.X	XX.X ± XX.X	XX.X ± XX.X	XX.X ± XX.X
		Median	XX.X	XX.X	XX.X	XX.X
		Min, Max	XX, XX	XX, XX	XX, XX	XX, XX
Visit 3 / Day 5						
Visit 4 / Day 8						

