**Listing 16.2.6.1- COVID-19 Symptom Assessment and Severity Score from Subject Diary**

Subject	Cohort	ND/ NA/ UNK	Day	Study Day	Date:Time	Cough	Sore Throat	Nasal Congestion	Headache	Chills/ Sweats	Muscle or Joint pain	Fatigue	Nausea	Fever (F)	SpO2 (%)	COVID-19 Severity Score	
Treatment:																	
xxxx				Day 1- Assessment 1		1											
				Day 1- Assessment 2		1											
				Day 2- Assessment 1		2											

COVID-19 Symptom: 0=None, 1=Mild, 2=Moderate, 3=Severe. Study Day is calculated relative to date of first treatment. Day 1 is the day of first treatment.  
O:\Studies\ EmitBio\EB-P20-01\Biometrics\Programs\Listings\xxx.sas ran on Month Day, Year at hh:mm on data from Month Day, Year

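### The protocol names the diary card as the source for local reactions after Day 1, but the diary as described has no local-reaction item, so brief reactions after home treatments may be under-recorded

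*Protocol*

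**What the plan says.** - **Source named in Protocol 9.2.** "Reactogenicity assessments will be performed on Day 1 in the clinic on days 3, 5, 8, and 14 by subjects' diary card entries". The sentence seems to lack a connecting word, but on either reading the post-Day 1 information comes from the diary. Protocol 6.3 also assesses tolerability at visits by "review of study subjects' daily diary cards for potential TEAEs, and oral cavity examination and targeted physical examination, as required".
- **What the diary holds.** Under Diary Cards in Protocol 9.2, subjects are to "fill out diary cards twice daily to assess their symptoms associated with disease progression and record the number of treatments completed". The content given is eight COVID-19 symptoms scored 0 to 3, temperature, oxygen saturation, shortness of breath and a treatment count. SAP Listing 16.2.6.1, "COVID-19 Symptom Assessment and Severity Score from Subject Diary", has columns for the symptoms, fever, SpO2 and the severity score.
- **Solicited reactions in Protocol 9.2.2.** Four items are listed: illumination-site pain, erythema, edema/induration, and any other oral mucosal finding. They "will be collected by direct questioning of study subjects", throughout the study.
- **SAP Table 14.3.2 note.** "Reactogenicity assessed after illumination for treatments performed at the site on Visits 1, 2, and 3".
- **Use of the data.** Protocol 4.1.2 lets the Safety Monitoring Committee consider the lower-dose cohort if "patterns of device-related adverse events, including application site reactions, are observed in Cohort A". Protocol 8.5.1 pauses enrollment when three or more subjects have related Grade 2 or higher events, local ones included, in the same MedDRA grouping.

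**The concern.** A site that follows 9.2 literally would look for local reactions on a form that, as described, has no place for them. A site that follows 9.2.2 would ask the subject. Neither section says which treatments the answer at a visit must cover, and the Table 14.3.2 note points at Visits 1 to 3 to the supervised treatment only. Most treatments are taken at home, and Protocol 5.2.1 expects local effects to be mild and transient, so a reaction can be over before anyone asks or looks.

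Local tolerability is a main safety result of a dose-finding study and one of the inputs to the cohort decision. It should not depend on which section a site happens to follow.

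**Working it through.** **1. Treatment count.** Two per day for 7 days (Protocol 4.1.1): 2 × 7 = 14. This reproduces the denominator of the compliance rule in Protocol 10.3 (11 of 14; 0.75 × 14 = 10.5, rounded up to 11).

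**2. On site and at home.** The footnotes to the Schedule of Activities place one treatment on site on each of Days 1, 3 and 5. On site: 3/14 = 21.4%. At home: 14 − 3 = 11, and 11/14 = 78.6%.

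**3. Home treatments by interval** (nominal visit days, on-site treatment first that day):

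| Interval | Home treatments | Scheduled call between |
|---|---|---|
| Day 1 to Day 3 visit | 1 + 2 = 3 | Day 2 |
| Day 3 to Day 5 visit | 1 + 2 = 3 | Day 4 |
| Day 5 to Day 8 visit | 1 + 2 + 2 = 5 | none |
| Total | 11 | |

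**4. Solicited items against the diary.** None of the four items in 9.2.2 appears in the diary description in 6.3 or 9.2, or as a column of Listing 16.2.6.1. The nearest diary item is sore throat, which is a COVID-19 symptom.

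**5. What happens to throat discomfort entered as sore throat.** Under Protocol 9.2.1, new or worse signs consistent with mild to moderate COVID-19 in the first 3 days are not recorded as TEAEs. That period holds 2 × 3 = 6 of the 14 treatments. Of these 6, two are on site (Days 1 and 3) and four at home. From Day 4 such a symptom is a TEAE only if moderate or greater, and the investigator decides whether to attribute it to COVID-19 or the device. Sore throat is therefore not a substitute for a site-pain item.

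**6. What Table 14.3.2 can show.** The note covers Visits 1 to 3. It does not say that the Visit 2 and Visit 3 rows include the 3 + 3 = 6 home treatments since the preceding visits. The Day 8 row has no on-site treatment behind it, so for the last five treatments it rests on recall or on findings still present.

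**7. What cannot be computed.** The documents give neither a local-reaction rate for these doses nor the share of reactions that subjects would recall. Any figure for under-recording would simply return the values assumed.

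**The case against.** The strongest reply is that the diary is not the only route.

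- Protocol 9.2.2 has staff ask about these reactions throughout the study and record them on the e-CRF.
- The interim history in 9.2 covers what has changed since the last visit, which supplies a look-back over home treatments.
- SAP Listing 16.2.9.3 carries all four items by visit.
- The schedules have reactogenicity and oropharyngeal rows, and Protocol 6.4 adds an oral examination by the investigator.
- The calls on Days 2 and 4 document adverse events.

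All of this stands. A reader might infer that home reactions go uncollected; the documents do not support that. What remains is that questions and calls rely on memory, and an examination sees only what persists.

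Four further limits also stand:

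- **The card has not been seen.** Listing 16.2.6.1 is not a full inventory: it has no shortness-of-breath or treatment-count column, although 9.2 covers both under Diary Cards. SAP section 6 calls the displays examples. An item on the real card cannot be ruled out.
- **Sources.** A reader might count three competing sources. The Table 14.3.2 note gives timing, not a source, and is compatible with direct questioning.
- **Sore throat.** A reader might conclude that device-related throat pain is simply counted as COVID-19. Section 9.2.1 leaves moderate or greater events from Day 4 to the investigator's attribution, and the five treatments between the Day 5 and Day 8 visits all fall in that period.
- **Dose step.** A reader might infer that the cohort decision would be wrong or the higher dose would look too well tolerated. This is not shown. The pausing rule needs related Grade 2 or higher events, which by the protocol's definition interfere with daily activities and are less likely to be forgotten over about three days.

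**Conclusion.** The point holds as an inconsistency with a limited consequence. The source named in 9.2 cannot, as described, hold the data; 9.2.2 names another; and the Table 14.3.2 note ties the Visit 1 to 3 rows to supervised treatments. Mild, brief reactions after the 11 of 14 home treatments may be under-recorded, chiefly after the five between the Day 5 and Day 8 visits. Throat discomfort entered as sore throat may go unrecorded as a TEAE in the first 3 days and, from Day 4, if less than moderate.

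This rests on nominal visit days and on the diary being as the protocol describes it. If the card already has the items, the protocol description and the SAP listing still need correcting. The documents do not establish a bias between doses or arms, or an effect on the pausing rule. The change is worth making because it is cheap and the card is already filled in twice a day.

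**What to change.** 1. Add the four solicited items of Protocol 9.2.2 to the twice-daily diary card, or confirm that they are on it. Show them in the protocol's diary description and in SAP Listing 16.2.6.1.
2. Reconcile Protocol 9.2, Protocol 9.2.2 and the SAP Table 14.3.2 note so that they name the same sources, and state that each visit's questions cover all home treatments since the last contact.
3. Add a row to Table 14.3.2 for any reaction at any time during treatment, combining diary and visit findings.

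Cost: a form revision and protocol and SAP wording, a slightly longer card, and probably a higher recorded reaction rate in both arms. Dosing, sample size and the efficacy analysis do not change.
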